For the evaluation of the individual indicators, boys and girls from 1st to 6th grade of primary school will be selected at random from the attendance lists of the school groups. A written consent from parents will be requested (Appendix 6) and an assent from the participants (Appendix 7). In the case of the evaluation of environmental indicators in schools, all schools' principals will be invited to participate and a written consent will be requested (Appendix 8).

Inclusion and exclusion criteria for schools and participants

Students who have provided assent to participate and who have the informed written consent of parents or caregivers will be eligible. Children who have a physical or mental disability to participate the program will be excluded.

Measurements

Healthy diet. Two instruments will be used, a 24-hour recall to estimate the total diet of schoolchildren, and food weighing to estimate food consumption within the school environment.

24-hour recall. This instrument will be used to measure and evaluate the total diet of schoolchildren. A 24-hour recall will be applied to mothers, fathers, or caregivers of participants responsible for feeding and preparing meals at home (Appendix 9). The registration system used for the National Health and Nutrition Surveys will be used (Shamah-Levy *et al.*, 2018). The 24-hour recall consists of an interview in which participants are asked to remember and describe all the food and beverages consumed the day before the interview, from the first intake of any food or drink, up to the last food or drink consumed before sleeping (Shim, Oh and Kim, 2014). The adult responsible for feeding the child will be asked to name, describe and quantify the amounts of all the food and drinks consumed by the participant the previous day. The information collected will include the characteristics of the food or drink, including preparation method, brands and quantity consumed (considering edible portion and total proportion consumed). Food and beverages consumed at school or outside the home without the adult being interviewed will be reported by schoolchildren. The instrument will be applied by trained staff and will be collected with the use of a laptop, using a software to collect 24-hour recalls in the Mexican population.

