Since part of the objectives of Salud Escolar is to improve the quality of the schoolchildren's diet and reduce the consumption of highly processed foods, the information obtained from the 24-hour recall will be used to evaluate the consumption of fruits and vegetables, sugar sweetened beverages (SSBs), and highly processed foods. A comparison will be conducted between participants consumption against the recommendations established in the Dietary and Physical Activity Guidelines in the Context of Overweight and Obesity in the Mexican Population (Bonvecchio, 2015). The proportion of schoolchildren who consume fruits and vegetables, and ultra-processed foods as outcome variables will be estimated.

Food and drink consumption during recess. Trained staff will record the food and drinks consumed during recess (snack or lunch) to objectively measure food consumption at school. Schoolchildren will be asked to show their lunch and beverages (brought from home or purchased at school) and what is contained will be recorded and weighted. This process will allow the detailed recording of the consumption of food and beverages at school campus, and the evaluation of the changes in food and beverages brought from home and purchased at school.

Correct hydration.

To analyze the impact of Salud Escolar on water consumption, a Beverage Diary will be applied to participants from 3rd to 6th grade (Appendix 10). The diary has been previously used and validated in different studies carried out by the INSP among schoolchildren (unpublished data) (Safdie *et al.*, no date; Pérez, 2016). Participants will receive a hard copy of the diary and will be asked to complete it at

home during three days. Data will be coded in Excel format and the consumption of water and SSBs (ml/day) will be estimated based on previously standardized procedures (Salud, 2015).

Physical activity

Direct observation and accelerometry will be used to measure physical activity.

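### The recess food record is called consumption, but the procedure only weighs what children bring or buy and has no step to establish what they eat

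*Combined protocol and SAP*

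**What the plan says.** All of this is in section 7.3 of the combined protocol and SAP, under Measurements.

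- The opening of the healthy diet part names two instruments: a 24-hour recall for total diet, and "food weighing to estimate food consumption within the school environment".
- The paragraph on food and drink during recess opens with its aim: "Trained staff will record the food and drinks consumed during recess (snack or lunch) to objectively measure food consumption at school".
- The procedure follows in one sentence. Children are "asked to show their lunch and beverages (brought from home or purchased at school) and what is contained will be recorded and weighted".
- The result is then labelled: "This process will allow the detailed recording of the consumption of food and beverages at school campus". The same sentence gives a second use, "the evaluation of the changes in food and beverages brought from home and purchased at school".
- The paragraph just before, on the recall, says that "the information obtained from the 24-hour recall will be used to evaluate the consumption of fruits and vegetables", and makes the proportion of children who consume them an outcome. The recall collects "quantity consumed (considering edible portion and total proportion consumed". For school food the informant is the child: "Food and beverages consumed at school or outside the home without the adult being interviewed will be reported by schoolchildren".

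The study hypothesis on fruit and vegetables concerns daily consumption in the school environment and expects a rise of 6.7%. Table 6 gives 6.2% for the fruit and vegetable indicator. Neither place names the instrument.

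**The concern.** Weighing what a child shows gives the food available to that child. It becomes consumption only when what is left over is subtracted or eating is observed, and no such step is described.

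The gap matters because the programme acts on supply. Its activities in section 2.3 include a behaviour change campaign and supervision of the food and drink available at school. It could therefore change what is packed or sold in programme schools without an equal change in what is eaten, and a record of food shown would report that as a change in consumption.

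Recess weighing is also the only diet measure that the plan describes as objective. The recall depends on report by adults and children, and the beverage diary is filled in at home. Readers may therefore give the recess result particular weight.

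**Working it through.** The plan states no figure on this point, so there is none to reproduce. The check is a comparison of texts, followed by algebra on what the planned estimator does with the error.

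**1. Aim against procedure**

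| Element | What section 7.3 gives |
|---|---|
| Aim | Food and drink consumed at recess |
| Act performed | Child shows lunch and drinks; contents recorded and weighed |
| Leftovers weighed or coded | Not described |
| Eating observed | Not described |
| Label on the result | Consumption; also change in food brought and bought |
| Form cited | None |

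On the last row, the text cites an appendix for the recall (9), the beverage diary (10), the SOFIT observation (11) and the accelerometer materials (12 to 14), but none for recess weighing. It therefore points to no form that might hold a leftover step.

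**2. What difference in differences does with the error**

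Take the yes/no outcome. In each arm and period let b be the share of children who bring or buy fruit or vegetables, and u the share of those who eat none of it. Then:

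- the share shown is b;
- the share eating is b × (1 − u).

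Let D be the time-by-group contrast in b.

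- *Same u in both arms and at both times.* The contrast in eating is (1 − u) × D. The record reports D, so the effect is multiplied by 1/(1 − u). The error does not cancel, because it is proportional. Only an error of the same number of percentage points in every arm and period would drop out.
- *Habits of existing bringers unchanged, and a share u of the added children eat none.* The result is again (1 − u) × D.
- *Programme changes eating but not packing.* If b is unchanged and u falls from u0 to u1 in programme schools only, the record shows D = 0 while eating rises by b × (u0 − u1). The effect is then understated.

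**3. Size, on an assumed u**

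The documents give no value for u. The range below is an assumption. The planned differences of 6.7 and 6.2 points serve only as a scale for the rise in food shown, since the plan states them for children who consume.

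| Assumed u | 6.7 × (1 − u) | 6.2 × (1 − u) | Inflation 1/(1 − u) |
|---|---|---|---|
| 20% | 5.4 | 5.0 | 1.25 |
| 40% | 4.0 | 3.7 | 1.67 |
| 60% | 2.7 | 2.5 | 2.5 |

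The inflation factor does not depend on which of the two planned differences is used. For this outcome only children who eat none count towards u: a child who eats half a portion is still a consumer. For an outcome in grams, partial leftovers also count.

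**4. Reach**

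The recall asks for the amount and proportion eaten, so fruit carried home uneaten is not counted by design on that instrument. The fruit and vegetable proportion is described in the recall paragraph. The hypothesis, however, is set in the school environment, which is the setting given to food weighing. The plan does not say which of the two tests it.

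**The case against.** The strongest reply has four parts.

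1. *The aim already says consumed.* The sentence before the weighing step says that staff will record what is consumed, so a leftover check is unspecified and not ruled out. That stands. It would be too strong to say that the plan makes a single weighing at the start of recess; it states neither the number nor the timing. But an aim does not tell field staff what to do, and the only action described does not deliver it.

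2. *The fruit and vegetable outcome belongs to the recall.* This stands and limits the point. A reader might infer that fruit packed and taken home will be counted as eaten in the main fruit and vegetable result. The documents do not support that, because no text says that the recess weights test it.

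3. *Recording what is shown suits the second stated use.* It does. For change in food brought and bought, the procedure is the right one.

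4. *The bias is speculative in size and direction.* On size, this stands: a reader might take the multiples above as estimates, but they only restate an assumed u. On direction, it also stands, since a programme that leads children to finish what they already bring would be understated. The related argument that equal overstatement in both arms cancels does not stand, because a constant uneaten share scales the effect.

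**Conclusion.** The point holds as a gap between label and procedure. As written, the recess record measures food and drink brought or bought, and the plan calls it consumption. Difference in differences would not repair this if the programme changes packing or sales more than eating, and the bias could be in either direction.

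The size cannot be derived from the documents. The factor 1/(1 − u) rests on u being the share of added children who eat none of what they bring, with the habits of other children unchanged, or on u being the same in both arms and at both times.

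The problem extends to the school-environment fruit and vegetable hypothesis only if that hypothesis is tested with the recess weights, which the plan neither says nor excludes. This warrants a change to the text before baseline fieldwork, because leftovers not recorded at baseline cannot be recovered later.

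**What to change.** In section 7.3, under food and drink consumption during recess, choose one of two options.

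- *Measure consumption.* Weigh or code what is left at the end of recess, in the same way in both arms and at both baseline and endline, and define consumption as the amount shown minus the amount left. The cost is an extra entry on the form and some added field time. Staffing must be confirmed: the fieldwork paragraph gives each six-member team two people for accelerometry and anthropometry and four for the diary and recall, and assigns no one to recess weighing.
- *Relabel.* Name the outcome *food and drink brought or bought*, a use the plan already lists, and base conclusions on consumption on the 24-hour recall. This costs nothing in the field. The price is that consumption at school then rests on children's own reports.

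Under either option, state in the study hypothesis and in the data analysis paragraph which instrument tests the school-environment fruit and vegetable hypothesis. At the same time, reconcile the 6.7% there with the 6.2% in Table 6.

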- Promotion of physical activity by conducting quality physical education sessions, implementing active recreation strategies and active breaks. The SEP will be responsible of these strategies by general teachers (active breaks) and physical education teachers (physical education classes).
- Promote healthy hydration by SEP.
- Validation of a health-promoting school by SS supervisors.
- Delivery of hot breakfasts by DIF.

During the second phase (August 2020-July 2021) the program will be scaled to 14 states in the country where there are regions among the highest levels of marginalization including: Chiapas, Veracruz, Guerrero, Oaxaca, Yucatán, Hidalgo, San Luis Potosí, Puebla, Quintana Roo, Nayarit, Durango, Chihuahua, Campeche and Michoacán (Secretaria de Salud and Secretaría de Educacion Pública, 2019).

²⁹ Finally, in a third phase (August 2021 - July 2022) the program will be scaled nationwide. The implementation of the program will be carried out through SEP teaching staff (Secretaria de Salud and Secretaría de Educacion Pública, 2019).

3. Conceptual and theoretical framework

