7.3 Impact analysis (baseline measurement)

Considering that Salud Escolar aims at creating healthy school environments, the impact analysis will be focused on the evaluation of some individual and environmental indicators.

Study design

A quasi-experimental design with baseline and endline evaluation will be used in schools where the School Health Program will be implemented (intervention group), and in schools where the program will not be implemented (control group). Measurements will be made prior to the start of the school program (pre-intervention), and 10 months after its implementation (post-intervention).

Study hypothesis

Based on similar studies previously carried out in the school population (Carriedo *et al.*, 2013; Safdie, Jennings-Aburto and Lévesque, 2013; McKenzie, 2015), we hypothesized the following changes in the endline measurement among children exposed to Salud Escolar, in comparison with those in the comparison group (not exposed to the intervention program):

- water consumption will increase by 171 ml (Carriedo *et al.*, 2013),
- time engaged in MVPA will increase in total 10 minutes per day, with an increase of 4 minutes per day during school recess and 4 minutes per day during physical education classes (Haerens *et al.*, 2007),
- the percentage of girls/boys who consume fruits and vegetables daily in the school environment will increase by 6.7% (Safdie, Jennings-Aburto and Lévesque, 2013).

Sample size calculation

The impact analysis study will be carried out in 30 primary schools in Mexico City (Intervention group = 15; Control Group = 15). The number of schools included was defined to better identify the effect (with a small number of schools the effect of the intervention could be confused with the characteristics of the schools) (Soto-Estrada *et al.*, 2016). Other criteria considered were the short time available for data collection (no more than three months according to reports by the Ministry of Health based on their experience during the implementation of the Health in your School program), as well as the available funds.

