Table 6 presents the sample size necessary for hypotheses testing, considering a significance level of $\alpha = 0.05$, a statistical power of 80%, and a correlation of 0.2 between the basal and final measurements. Considering that the largest sample size required is the one to estimate the effect of the intervention on fruit and vegetable consumption ($n = 388$), a design effect of 2, and 20% losses to follow-up, it is estimated that a total of 980 girls and boys ($n = 490$ per intervention group) are needed.

A baseline measurement of 1000 girls and boys has been proposed. Considering the same assumptions of design effect and loss to follow-up, it was estimated that a sample size of 595 girls and boys is required for accelerometry measurements and the System for Observing Fitness Instruction Time (SOFIT).

Table 6 The sample size required to estimate expected differences

Indicator	Standard deviation	Expected difference	Sample size
Water consumption (ml/day)	631	171	384
MVPA (min/day)	40	10	248
MVPA (min/PE)	9	3.8	248
MVPA (min/recess)	12	3.9	244
Fruit and vegetable consumption (% of schoolchildren)		6.2%	388

Note. MVPA= moderate to vigorous physical activity; PE= physical education.

Schools selection

The intervention group schools will be selected randomly from the predefined list of 58 schools selected by the Ministries of Health and Education to participate in the first phase of implementation of Salud Escolar. The control group will be selected from a list of schools available in Mexico City provided by the Ministry of Education, where the program will not be implemented. Given that the selection of the 58 schools of the intervention group will not be at random, schools from the control group will be as similar as possible to those in the intervention group. Thus, it will be sought that the schools of both groups (i.e, intervention and comparison) are paired based on the following characteristics:

- Location: schools should be in the same geographical area < 5 km.
- Basic Geostatistical Area (BGA): within a similar BGA level
- Type of working day: in the same type of working day (regular, extended or full time)
- Hours: both in the morning or in the afternoon
- Size: schools from both groups will be expected to have a similar number of students and classes.

Participants

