Direct observation. This will be used to analyze the effect of Salud Escolar on the quality of physical education (PE) classes and active recess of the program (minutes of MVPA). The System for Observing Fitness Instruction Time (SOFIT) will be used to evaluate PE and an adapted version will be used to measure physical activity during recess. SOFIT is a comprehensive tool for evaluating physical education in terms of student physical activity levels, class context, and teacher or instructor behavior (McKenzie, 2015). This is a validated and reliable tool, which can be used in multiple contexts (McKenzie, 2015). Prior to the start of the lesson, target students will be selected. One student will be observed for 4 minutes, then the observer will focus on the other remaining students for 4 minutes (each) until class ends. Prerecorded verbal prompts on CDs, MP3s, or audiotapes will be used to help the observer to systematically follow up the class on a 10-second intervals basis throughout the class. During each registration interval, the observer records a code corresponding to the behaviors of interest (students, context, or teacher).

All data will be recorded in a specific format for subsequent analysis (Appendix 11). Data will be summarized by time (3 intervals = 1 minute), percentage of intervals or class time, or estimated energy expenditure. Comparisons may be made between different categories, between classes over time, or against established standards. The main variables to obtain from this observation method are:

- The physical activity levels of students: Minutes and % of the PE class in each of the intensities of physical activity (including minutes of MVPA), energy expenditure estimated per session (kcal/kg) and rate of the estimated energy expenditure (kcal/kg/min) (Department of Health & Human Services, 2018).
- Physical education schedule: frequency of sessions and adherence to the proposed schedule, scheduled duration and actual duration of the sessions.
- Context of the session: minutes and % of the session time spent in administrative matters, instruction, physical fitness, skill exercises, play time and others.
- Teacher behavior: % of the class that the teacher or instructor invests in promoting the activity during and outside of class time.

Accelerometry

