Actigraph GT3X + accelerometers (ActiGraph, LLC, Pensacola, FL, USA) will be used to assess the effect of the intervention on total physical activity (minutes per day of MVPA). Accelerometry is a method for objectively monitoring physical activity and providing rich data about users' physical activity intensities. Accelerometers will be distributed to a subsample of participants in schools by

trained staff who also will record allocation and collection of the devices (Appendix 12).

Participants will be asked to wear an accelerometer with a flexible belt, on the right side at the axillary midline, for at least 7 full days (plus one day of familiarization and the morning of the last day), including two weekend days. Wearing time will be at least for 7 days in order to maximize the number of participants with sufficient valid data (minimum wearing time of 4 days with 10 hours each day). Participants and their parents or caregivers will be explained to remove the accelerometer only during bedtime and water-based activities (e.g. swimming), clear information and a demonstration of wearing the device will be provided by trained staff (Appendix 14). To ensure the adequate use of accelerometers, a daily checklist (Appendix 13) will be used to record the use of the accelerometer every morning at the school by trained staff. This school visits will be an opportunity for the trained staff to clarify participants questions about the accelerometer. Phone messages and calls, and small incentives (stickers) at the time of verification by the staff will be used as compliance enhancing strategies.

The software ActiLife 6.13.4 will be used for accelerometer initialization prior to allocation and data download after collection. Daily MVPA will be estimated using an algorithm prepared by the research team. Freedson's cut-off points will be used to estimate the schoolchildren time per day spent at different intensities of physical activity (Department of Health & Human Services, 2018).

Other variables

Anthropometry

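### The accelerometer files are used only for whole-day MVPA, so recess MVPA rests on an adapted observation form alone and active breaks show only inside the daily total

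*Combined protocol and SAP*

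**What the plan says.** The Accelerometry subsection of 7.3 says that the devices "will be used to assess the effect of the intervention on total physical activity (minutes per day of MVPA". What follows concerns daily MVPA and time per day by intensity. No recess, class-time or school-hours window is named. A subsample wears the device through waking hours, apart from water activities, for at least 7 days including two weekend days. A record is valid with 4 days of 10 hours. Staff check wear at school every morning.

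The Direct observation subsection assigns minutes of MVPA in PE and recess to observers. SOFIT is used for PE, and for recess "an adapted version will be used to measure physical activity during recess". SOFIT is described as watching one child for 4 minutes and then moving to the next. The statement that the tool is validated refers to SOFIT itself.

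The strategy list in section 2.3 includes active breaks, assigned to "general teachers (active breaks", alongside PE and active recreation. Under Study hypothesis, total MVPA is expected to rise by 10 minutes per day, with "an increase of 4 minutes per day during school recess" and a further 4 in PE.

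**The concern.** Most of the expected activity effect lies in parts of the school day when the wearing children already have a device on, yet the plan takes no school-time outcome from those files. The recess hypothesis therefore depends on one instrument, an adaptation whose validity is not shown, coded by people on site. Active breaks fall outside both PE and recess observation. If they work, the only place to see it is a daily total that also contains evenings and weekends. At stake are the credibility of the recess result and the ability to say whether activity changed during the school day.

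**Working it through.** **1. The plan's own figure.** Inputs are n = 248 for whole-day MVPA (Table 6) and, from the sample size text, "a design effect of 2, and 20% losses to follow-up". 248 × 2 × 1.20 = 595.2, which reproduces the stated 595 for accelerometry and SOFIT together. (Dividing by 1 − 0.20 would give 496 / 0.80 = 620; that is a separate matter.) The schools are "Intervention group = 15; Control Group = 15", so 30 in all. Reading 595 as the total, 595 / 30 = 19.8, or about 20 wearers per school.

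**2. Where the effect is expected.** From the Study hypothesis: (4 + 4) / 10 = 80% in recess and PE. From Table 6: (3.9 + 3.8) / 10 = 77%. The Table 6 rows are per recess and per PE class, so the second figure equals a daily share only if each occurs once a day.

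**3. What measures what.**

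| Component | Hypothesised rise | Source of MVPA minutes | Own outcome |
|---|---|---|---|
| Whole day | 10 min/day | Accelerometer | Yes |
| Recess | 4 min/day | Adapted SOFIT only | Yes, observed |
| PE | 4 min/day | SOFIT only | Yes, observed |
| Active breaks | None stated | Inside the whole-day total | No |
| School hours as a whole | None stated | Inside the whole-day total | No |

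**4. What each source holds for recess.** Section 7.3 converts three coded intervals to one minute, so one 4-minute turn gives 4 × 3 = 12 intervals per child, from which minutes per recess must be extrapolated. This assumes that the recess version keeps SOFIT's rotation; no other rule is given. Recess length, the number of observers and the number of recesses observed are not stated, and the Fieldwork paragraph assigns no team member to observation. Nor do the documents say whether the observed children wear devices or are observed again at endline.

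A device record covers the whole of every recess on each school day worn, for an identified participant. But the validity rule sets no minimum of school days: 4 valid days less 2 weekend days leaves as few as 2. The relative precision of the two measures therefore cannot be computed from the documents.

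**5. How observer error would enter.** The effect is the time-by-group interaction over two time points. At baseline there is no programme to see. If endline coding in programme schools is shifted by *b* minutes relative to control schools, the interaction estimates the true effect plus *b*. The expected recess effect is about 4 minutes. The documents give no basis for a value of *b*, which may be zero.

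**The case against.** The strongest reply is that no stated hypothesis lacks a measure: total, recess and PE MVPA each have one. SOFIT uses prompted interval coding and is described as validated, so calling it merely subjective would be unfair. This stands. What remains is that the validation statement does not extend to the recess adaptation. The protocol also presents only the first stage, so windowed outcomes can still be set before endline. That is true and is why the fix is timely, but bell times must be captured for both rounds.

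Several stronger readings are tempting and are not supported:

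- *All school-hours activity is left to observers.* They cover only PE and recess; the rest of the school day is inside the device total.
- *Observers are known to be unmasked.* The documents are silent. That they could tell the arm at endline is an inference, plausible for a visible school-level programme.
- *The files can isolate active breaks.* They cannot without a log of when breaks occur. Bell times give only school-hours MVPA that includes them.
- *Recess data would need fewer children.* Table 6 implies 3.9/12 = 0.325 SD for recess against 10/40 = 0.25 SD for the whole day. But recess is already a planned outcome, so this does not measure what device data would add, and the instrument behind the recess SD is not stated.
- *Devices capture far more child-recesses than observers do.* The 595 is set for SOFIT as well, and observation effort is unspecified.
- *Weekend MVPA could test parallel trends.* Section 2.3 says the programme also aims to raise activity outside school hours and includes a behaviour change campaign, so a weekend effect could be programme impact. The same text limits how far evening time counts as dilution.

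**Conclusion.** The point holds as a missed, low-cost outcome that should be added; it does not invalidate the design. On the hypothesis as written, 80% of the expected MVPA gain lies in recess and PE, yet the device data are not summarised for any part of the school day. The recess hypothesis rests on a single adapted instrument with no cited validation and no statement on masking. Active breaks have no outcome of their own. The gain in precision or reduction in bias from device-based recess MVPA cannot be quantified from the documents. The conclusion assumes that wearers keep devices on at school, as instructed, and that timetables can be recorded.

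**What to change.** In the Accelerometry subsection of 7.3:

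- Record each school's bell times during the existing morning wear checks, in both measurement rounds.
- Prespecify, before endline, two further outcomes from the same files: recess MVPA, as the objective measure for the recess hypothesis, reported beside the observed one; and school-hours MVPA, stated to include active breaks without isolating them.
- Set a minimum number of valid school days for these two outcomes, in addition to the present wear rule.
- Exclude any recess in which that child's lunch was being weighed, since the weighing itself interrupts activity.
- Keep whole-day MVPA, and keep SOFIT for PE and lesson context, which a device cannot show.
- Weekend MVPA may be reported descriptively, but not as a negative control.

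The cost is noting bell times, extra scoring of files already planned, and two more outcomes to report, available for the wearing subsample only. No additional devices, children or visits are needed.
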